1. SYNOPSIS

Protocol Title: A single-centre, randomized, double-blind, dose-ascending, placebo-controlled study to evaluate the safety, tolerability, and pharmacokinetics of oral TID doses (one day) of GSK2982772 in Japanese healthy male subjects

Short Title: Phase I study of GSK2982772 in Japanese healthy male subjects

Rationale:

This study is the first administration of GSK2982772 to Japanese. The purpose of this study is to evaluate the safety, tolerability, and pharmacokinetics (PK) of oral doses of TID doses for one day with GSK2982772 in Japanese healthy male subjects. GSK2982772 or placebo will be administered at 0 hr (the first dosing), 7 hr (the second dosing) and 14 hr (the third dosing) on Day 1 in each period. The intention of this study is to provide sufficient confidence in the safety of the molecule to inform progression to further repeat dose studies in patients. The dose range proposed in this study is based on a low starting dose escalating to the highest dose that is intended for the Phase 2b dose range study.

Objectives and Endpoints:

Objectives	Endpoints
To assess the safety and tolerability of TID doses for one day of GSK2982772 in Japanese healthy male subjects	Adverse events (AEs) Change in laboratory values (clinical chemistry, haematology and urinalysis), 12-lead ECG and cardiac telemetry, vital signs (blood pressure, pulse rate, and body temperature) Physical examinations, including neurological examinations
To characterise the PK profile of TID doses for one day of GSK2982772 in Japanese healthy male subjects	Derived PK parameters for GSK2982772, including area under the plasma drug concentration versus time curve over 24 hr (AUC(0-24)) and AUC over each dose interval (i.e. AUC(0-7), AUC(7-14) and AUC(14-24)), maximum observed plasma drug concentration (C _{max}) following each dose, time to maximum observed plasma drug concentration (T _{max}) following each dose, terminal half-life (t _{1/2}) following the third dose, observed trough plasma drug concentrations (C ₀ , C ₇ , C ₁₄ and C ₂₄), where data allow

Overall Design:

This study will be a double-blind with respect to subjects, investigators and site staff (with the exception of the unblinded site pharmacist), TID oral doses for one day,

ascending dose, randomized, placebo-controlled, 4-way crossover study, shown as the table below;

Group	N	Period 1	Period 2	Period 3	Period 4
A	3	Placebo, TID	60 mg, TID	120 mg, TID	240 mg, TID
B	3	60 mg, TID	Placebo, TID	120 mg, TID	240 mg, TID
C	3	60 mg, TID	120 mg, TID	Placebo, TID	240 mg, TID
D	3	60 mg, TID	120 mg, TID	240 mg, TID	Placebo, TID

Number of Participants:

Sufficient Japanese healthy male subjects will be enrolled such that up to approximately 12 subjects complete dosing and critical assessments.

If subjects prematurely discontinue the study, additional replacement subjects may be randomized in order to guarantee that sufficient subjects are treated with GSK2982772 at any given dose before escalating to the following dose. Replacement subjects will be assigned to the same treatment sequence and start from the period to be replaced at the discretion of the GSK and in consultation with the principal investigator.

Sentinel Dosing:

The doses will be staggered such that for each dose, on Day 1 of Period 1, 2 and 3, two of the 12 subjects will be randomized to treatment (one subject will receive GSK2982772 and one subject will receive matched-placebo). Assuming 2 subjects are dosed on Day 1 and assuming adequate safety (AEs, clinical labs, vital signs, 12-Lead ECGs and Cardiac telemetry) in the judgment of the principal investigator and GSK Medical Monitor through at least 24 hrs after their third dose on Day 1, the remaining subjects may be randomized to dosing in that period.

Treatment Groups and Duration:

Screening	Within 30 days prior to the first dose on Day1.
Treatment Period	
The study will be comprised of four study periods each at least 7 days in duration with subjects in-house for 4 nights (through 72 hrs after the first dose). During each treatment period, subjects will be admitted to the unit the day before dosing and will be discharged after completion of the 72 hrs post-dose assessments.
 
Each subject will receive oral TID doses of GSK2982772 in each treatment period. For TID dosing, GSK2982772 or placebo will be administered at 0 hr (the first dosing), 7 hr (the second dosing) and 14 hr (the third dosing) on Day 1 in each period. On Day 1, subjects will fast 8hr overnight prior to first dose. A breakfast will be served approximately 2hr after first dose. Lunch and dinner will be served between 2 to 3hr prior to second and third doses, respectively.

Washout Period	Will be at least 7 days between treatment period doses for an individual

	subject.
Follow-up	At least 7 days, and no greater than 14 days after last study treatment administration. If warranted, additional follow-up visits may be scheduled.

2. SCHEDULE OF ACTIVITIES (SoA)

Protocol waivers or exemptions are not allowed with the exception of immediate safety concerns. Therefore, adherence to the study design requirements, including those specified in the Schedule of Activities (SoA) tables, are essential and required for study conduct.

The Study Reference Manual (SRM) will provide the site personnel with administrative and detailed technical information that does not impact subject safety.

This section lists the procedures and parameters of each planned study assessment. The exact timing of each assessment is listed in the SoA tables.

The following points must be noted:

- If assessments are scheduled for the same nominal time, THEN the assessments should occur in the following order:
 1. 12-Lead ECG
 2. Vital Signs
 3. Blood Draws

Note: The timing of the assessments should allow the blood draw to occur at the exact nominal time.

A table defining the allowed variance in timings of assessments without being considered a protocol deviation will be included in the SRM.

Time and Events Table for Screening and Follow-up Assessments

Procedure	Screening ¹	Follow-up Visit ²	Notes
Outpatient Visit	X	X	
Informed Consent	X		
Medical/medication/drug /alcohol history	X		
Demographics	X		
Physical Examination	X	X	Additional examinations may be performed, by the Investigators, as deemed necessary.
Drug screen	X		Additional tests may be performed by the Investigators, as deemed necessary. Tests will be conducted within site specified standards.
Syphilis, Human immunodeficiency virus (HIV), Human T-cell leukemia virus type 1 (HTLV-1), Hepatitis B (Hep B) and Hepatitis C (Hep C) screen	X		
Tuberculosis (TB) Test	X		Conducted at the standard practice of the site.
X-ray Test	X		Anterior & lateral chest X-ray will be taken.
Hema/Chem/Urinalysis tests	X	X	
Height and weight	X		
12-lead ECG and vital signs	X	X	Vital signs to include pulse rate (PR), blood pressure (BPs) and temperature.
AE Review	X	X	All Serious Adverse Effects (SAEs) will be collected from the signing of the informed consent form (ICF) until the follow-up visit at the time points specified. All AEs will be collected from the start of treatment until the follow-up visit at the time points specified.
Concomitant Medication Review	X	X	

1: Within 30 days prior to the first dosing

2: Follow-up Visit to occur at least 7 days, and no greater than 14 days after last study treatment administration. If a participant withdrew from the study after received GSK2982772 or placebo dose, the safety assessments listed at follow-up visit will be required.

Detailed Time and Events Table for Days 1-4 (common Period1-4)

Procedure ¹	Day -1	Day 1																									
		Pre-dose	0	20 min	40 min	1 hr	1.5 hr	2 hr	3 hr	4 hr	5 hr	7 hr	7 hr 20 min	7 hr 40 min	8 hr	8.5 hr	9 hr	10 hr	11 hr	12 hr	14 hr	14 hr 20 min	14 hr 40 min	15 hr	15.5 hr		
Admission	X																										
Physical Examination	X	X						X				X ⁶													X ⁶		
Hema/Chem/Urinalysis tests	X																										
Vital signs ²		X						X				X ⁶												X ⁶			
12-lead ECG		X						X				X ⁶											X ⁶				
Cardiac telemetry ³		<=====																									
PK blood sampling		X		X	X	X	X	X	X		X	X ⁷	X	X	X	X	X	X	X		X	X ⁷	X	X	X	X	X
Neurological Examination	X							X																X ⁸			
Study Treatment			X									X											X				
Pharmacogenetic Sampling (PGx) ⁴		<=====																									
Meals Served	X							X ⁹			X ⁹											X ⁹					
AE Review ⁵		<=====																									
Concomitant Medication Review		<=====																									
Discharge																											

Procedure ¹	Day 2								Day 3		Day 4
	16 hr	17 hr	19 hr	22 hr	24 hr	28 hr	32 hr	36 hr	48 hr	60 hr	72 hr
Admission											
Physical Examination					X			X	X		X
Hema/Chem/Urinalysis tests											X
Vital signs ²					X				X		X
12-lead ECG					X				X		X
Cardiac telemetry ³	=====>										
PK blood sampling	X	X	X	X	X	X	X	X	X	X	X
Neurological Examination					X				X		X
Study Treatment											
Pharmacogenetic Sampling (PGx) ⁴	=====>										
Meals Served						X ¹⁰		X ¹⁰	X ¹⁰	X ¹⁰	
AE Review ⁵	=====>										
Concomitant Medication Review	=====>										
Discharge											X

1: In this study, baseline is Day -1 and Day 1 pre-dose tests.

2: Vital signs include PR, BPs and temperature.

3: Only 24 hrs following the first dose administration

4: A PGx blood sample will be collected at any time during the study after randomization and provided informed consent for genetic reserch. The participation is optional for each subject.

5: All SAEs will be collected from the signing of the ICF until the follow-up visit at the time points specified. All AEs will be collected from the start of treatment until the follow-up visit at the time points specified.

6: Physical Examination, Vital signs and 12-lead ECG of 7hr and 14hr time point are to be performed prior to second or third dose.

7: PK blood sampling of 7hr and 14hr time point are to be performed right prior to second or third dose.

8: Neurological Examination of 14hr time point are to be performed prior to third dose.

9: On Day 1, breakfast will be served approximately 2hr after the first dose, lunch will be served between 2 to 3 hr prior to second dose and dinner will be served between 2 to 3 hr prior to third dose.

10: On Day 2-3, meal will be served per unit schedule. Mealtime will be described in SRM.

3. INTRODUCTION

GSK2982772 is a first-in-class highly selective, RIP1 kinase inhibitor being developed for the treatment of inflammatory bowel disease (IBD), plaque psoriasis (PsO), rheumatoid arthritis (RA) and other disease conditions.

3.1. Study Rationale

The purpose of this study is to evaluate the safety, tolerability, and pharmacokinetics (PK) of oral doses of T1D doses for one day with GSK2982772 in Japanese healthy male subjects. This study is the first administration of GSK2982772 to Japanese.

3.2. Background

GSK2982772 is a first-in-class, highly selective, small molecule inhibitor of RIP1 kinase. RIP1 is a member of the receptor-interacting Ser/Thr kinase family containing an amino-terminal kinase domain, an intermediate domain and a carboxy-terminal death domain. RIP1 is a key signalling node which plays an essential role in inflammation and cell death in response to signals including TNF family cytokines, ligands for TLR3/TLR4, sensors of viral infection, and interferons [Ofengeim, 2013]. Through tight regulation by ubiquitylation, deubiquitylation and interaction with its receptors, RIP1 has dual roles as a kinase and a scaffolding protein, and serves as an upstream checkpoint for both cell death and survival [Ofengeim, 2013]. Detailed understanding of RIP1 kinase function has not been fully elucidated, but it is known that RIP1 exerts its signalling functions through both its catalytic kinase activity and by acting as a scaffolding protein for signalling complexes. Recent work has demonstrated that RIP1 catalytic kinase activity can regulate TNF-mediated necroptosis [Ofengeim, 2013] and noncanonical apoptosis [Wang, 2008, Dondelinger, 2013]. In addition, the production of certain inflammatory cytokines can be regulated by RIP1 kinase activity. In contrast, RIP1's scaffolding function acts to facilitate other immune processes including TNF mediated classical apoptosis and Nuclear factor-kappaB (NF- κ B)-signalling [Ofengeim, 2013, Humphries, 2015]. With this, an inhibitor of RIP1 kinase activity with GSK2982772 may fill a unique niche in the treatment of inflammatory conditions (eg. PsO, RA and IBD) through multiple mechanisms, including inhibition of inflammation-induced cell death (necroptosis and apoptosis) and inhibition of the production of certain pro-inflammatory cytokines.

A range of nonclinical studies have been conducted to support the administration of GSK2982772 to humans [GlaxoSmithKline Document Number 2014N204126_04].

The First Time in Human (FTiH) study which was single (fed and fasted) and repeat dose escalation study (Study 200975) of GSK2982772 in healthy male subjects of predominantly White/Caucasian/European heritage in United Kingdom, 67 subjects were exposed to active treatment. GSK2982772 was well-tolerated up to 120 mg BID for 14 days, with no deaths or other non-fatal SAEs being reported.

3.3. Benefit/Risk Assessment

More detailed information about the known and expected benefits and risks and reasonably expected adverse events of GSK2982772 may be found in the IB. The following section outlines the risk assessment and mitigation strategy for this protocol.

Respiratory effects	
Non-Clinical data: In the single dose Safety Cardiovascular and Respiratory Study in monkeys, a decrease in minute volume (minute volume: MV) and respiratory rate was observed at all doses (10, 100, and 300 mg/kg). These findings were noted to be reversible and mild in severity. In a 14 days repeat dose Safety Respiratory Study in monkeys, no respiratory effects on total pulmonary ventilation (MV) or respiratory rate were observed at doses of 1 or 10 mg/kg/day. See IB for GSK2982772 [GlaxoSmithKline Document Number 2014N204126_04].
 
Clinical data: In the FTiH study, repeat doses of GSK2982772 up to 120 mg BID were administered 14 days in 36 healthy male subjects. Extensive respiratory monitoring with end-tidal CO₂ (ETCO₂), oxygen saturation (SpO₂) and nocturnal respiratory rate monitoring was performed. No SAEs occurred, and no drug associated respiratory-related AEs were identified.
	
Subject Monitoring:
 
 • Subjects should be monitored for standard respiratory-related AEs. • Vital signs will be monitored during study visits.

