9.3.1. Physical Examinations

- A complete physical examination will include, at a minimum, assessments of the Skin, Cardiovascular, Respiratory, Gastrointestinal and Neurological systems. Height and weight will only be measured and recorded on screening.
- Investigators should pay special attention to clinical signs related to previous serious illnesses.

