9.3.3. Vital Signs

- Axillary temperature, pulse rate, and blood pressure will be assessed.
- Blood pressure and pulse measurements will be assessed supine position with a completely automated device. Manual techniques will be used only if an automated device is not available.
- Blood pressure and pulse measurements should be preceded by at least 5 minutes of rest for the participant in a quiet setting without distractions (e.g., television, cell phones).
- Vital signs will be measured in a supine position after 5 minutes rest and will include temperature, systolic and diastolic blood pressure, and pulse rate.

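### The respiratory risk row relies partly on vital signs, but no vital sign defined in the protocol is a respiratory measurement

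*Protocol*

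**What the plan says.** The respiratory effects row of the risk table (Protocol Section 3.3) reports that in a single-dose monkey study "a decrease in minute volume (minute volume: MV) and respiratory rate was observed at all doses (10, 100, and 300 mg/kg"). It adds that the effect was mild and reversible, and that a 14-day monkey study at 1 and 10 mg/kg/day showed no effect on minute volume or respiratory rate. For man, it describes end-tidal CO2, oxygen saturation and nocturnal respiratory rate in the first-in-human study, at repeat doses up to 120 mg BID, with no drug-associated respiratory AEs.

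The row gives two monitoring measures: "Subjects should be monitored for standard respiratory-related AEs", and "Vital signs will be monitored during study visits".

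Vital signs are defined in several places, always with the same content:
- Protocol Section 2, treatment-period schedule, footnote 2: "Vital signs include PR, BPs and temperature".
- Protocol Section 2, screening and follow-up table: "Vital signs to include pulse rate (PR), blood pressure (BPs) and temperature".
- Protocol Section 9.3.3: "Axillary temperature, pulse rate, and blood pressure will be assessed", and again that they "will include temperature, systolic and diastolic blood pressure, and pulse rate".
- The endpoint tables in the Synopsis, Protocol Section 4 and SAP Section 2.2 list the same three measures.

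The physical examination (Protocol Section 9.3.1) must include "assessments of the Skin, Cardiovascular, Respiratory, Gastrointestinal and Neurological systems". No respiratory measurement is named.

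**The concern.** The risk is a change in two measurable quantities, respiratory rate and minute volume. One of the two measures put against it, vital signs, contains neither. The row reads as though scheduled readings will follow the risk, but Section 9.3 and the schedule do not deliver that.

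Two things are at stake. The study report could describe respiratory AEs but could not compare respiratory rate on active drug with placebo, although each participant has a placebo period. The sentinel and escalation reviews would also see respiratory information only if someone had recorded an AE. Safety is a study objective, and this is the first administration to Japanese subjects, at a top dose above the one for which respiratory measurements are described.

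**Working it through.** **1. What is measured, against what the risk row needs**

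| Source of respiratory information | Content | Reaches escalation review? | SAP display? |
|---|---|---|---|
| Vital signs (Protocol 2, 4, 9.3.3) | Pulse rate, blood pressure, temperature | Yes (5.3, 5.4, 8.1.1) | Tables 2.20–2.21, Listings 34–35; none respiratory |
| Physical examination (Protocol 9.3.1) | Respiratory system, qualitative | Not in the minimum list in 5.4, nor in 5.3 or 8.1.1 | None in SAP 7.3 or Appendix 9 |
| AE reporting (Protocol 9.1) | Whatever is noticed or reported; open-ended questioning preferred (9.1.2) | Yes | Tables 2.1–2.4, Listings 14–18 |
| Respiratory rate, oxygen saturation, end-tidal CO2 | Not scheduled | No | None |

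The SAP's limits of potential clinical importance for vital signs (Section 9.7.3) cover systolic pressure, diastolic pressure and heart rate only.

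**2. Number and timing of readings (protocol schedule)**

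Vital signs: pre-dose, 2, 7, 14, 24, 48 and 72 h, which is 7 per period. Over four periods, 7 × 4 = 28 per participant.

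Physical examination: Day -1, pre-dose, 2, 7, 14, 24, 36, 48 and 72 h.

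The 7 h and 14 h assessments come before the next dose (footnote 6). With a median Tmax of about 1.5 to 2.5 h (Protocol Section 3.2), only the 2 h time point lies near a peak. Neither vital signs nor a physical examination is scheduled between 14 h and 24 h, the interval after the third dose.

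**3. Dose relative to the described respiratory monitoring**

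The plan's own figure reproduces: 3 × 240 mg = 720 mg/day (Protocol Section 5.7).

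- First-in-human maximum with respiratory monitoring: 2 × 120 mg = 240 mg/day.
- Daily-dose ratio: 720 / 240 = 3.0.
- Per-dose ratio: 240 / 120 = 2.0.

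The documents give no AUC or Cmax at 120 mg BID, so an exposure ratio has to be assumed. A linear one-compartment oral model was run with half-life 2, 3 or 6 h and Tmax 1.5 or 2.5 h, comparing 240 mg at 0, 7 and 14 h with 120 mg every 12 h:

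- AUC(0-24) ratio: 2.93 to 2.98 against BID Day 1; 2.41 to 2.95 against BID Day 14.
- Cmax ratio: 2.23 to 2.73.

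These are modelled values. Dose proportionality is reported only for single doses of 0.1 to 120 mg and, on repeat dosing, up to 120 mg BID (Protocol Section 3.2).

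**The case against.** The strongest reply is that the passages do not strictly conflict. The risk row says vital signs will be monitored, and they will be; it never says they include respiratory rate. The respiratory system is examined repeatedly, respiratory AEs are to be watched for and all AEs go to escalation review, participants stay in-house for four nights, and significant respiratory disorder is an exclusion. The nonclinical signal was mild and reversible.

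Most of this stands, and it limits the point. A reader might infer that the monitoring cannot detect a respiratory effect, or that escalation review has no respiratory information. Neither follows: AE reporting and the examination exist. The supportable statement is that no respiratory measurement is scheduled and that the examination is qualitative, undisplayed and outside the minimum review set. The reply does not explain why vital signs are listed against this risk.

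Two further inferences also fail.

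- **That respiration was last studied in man at a third of this exposure.** Study 205184 has completed one-day sessions of 240 mg TID and 360 mg BID, both 720 mg/day, and these were tolerated. Whether respiration was measured is not stated. Three-fold is a ratio of daily doses, not of observed exposures.
- **That this trial exceeds a monkey effect exposure by a known multiple.** One can scale the 13-week AUC of 48.4 µg·h/mL at 30 mg/kg/day down to 10 mg/kg, giving 48.4 / 4 = 12.1 or 48.4 × 10/30 = 16.1, and set the predicted 40.2 against them (40.2 / 16.1 = 2.5; 40.2 / 12.1 = 3.3). But these approximate repeat-dose exposure at 10 mg/kg/day, the level at which the 14-day study saw no respiratory effect. No AUC is given for the single-dose study that did see one.

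**Conclusion.** The point holds in a limited form. Vital signs are cited as monitoring for a fall in respiratory rate and minute volume, yet all 28 scheduled readings per participant lack a respiratory value, and no respiratory quantity is measured elsewhere. The top dose is 3-fold by day and 2-fold per dose above the highest for which the protocol describes respiratory measurement.

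This is an inconsistency with a cheap remedy, not a threat to the validity of the trial. The conclusion rests on the definitions in Protocol Sections 2, 4 and 9.3.3, which agree with each other, and on the absence of any respiratory measurement from Section 9.3. It does not depend on the modelled exposure ratios. Rows of the risk table next to this one were not available for checking; they could add wording, but the schedule and Section 9.3 determine what is collected.

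**What to change.** Reconcile the respiratory risk row with Protocol Sections 2, 4 and 9.3.3. There are two ways; the choice is the sponsor's.

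1. **Give the named instrument a respiratory value.** Record respiratory rate at the seven existing vital-sign readings per period, during the five-minute supine rest Section 9.3.3 already requires. Amend Section 9.3.3, both schedule tables and the endpoint tables in the Synopsis, Protocol Section 4 and SAP Section 2.2. Carry the variable into SAP Tables 2.20–2.21 and Listing 34. SAP Section 7.3.1 already summarises each vital-sign parameter and its change from baseline by treatment, so no new method is needed, and the crossover supplies a within-subject placebo comparison.
2. **Correct the claim.** Stop citing vital signs as respiratory monitoring and state that it rests on AEs and the physical examination.

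Option 1 costs one CRF field and about one minute per reading, or 28 × 1 = about 28 minutes per participant over four periods, with no new visit. It has limits: respiratory rate is not minute volume, only the 2 h reading is near a peak, and none falls between 14 h and 24 h. It would supply descriptive data, not proof that there is no effect. Option 2 is a wording change only.
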